7.2 Protocol deviations

Protocol deviation management for this trial is detailed in the trial specific Protocol Deviation and Non-compliance Management Plan. According to this plan, protocol deviations or site non-compliance are documented concisely in the Clinical Trial Management System (CTMS) and periodically reviewed as part of the project oversight by a wider study team.

Protocol deviations are failures to adhere to the inclusion/exclusion criteria and protocol requirements and will be classified into important protocol deviations and not important protocol deviations.

- Important protocol deviations are a subset of protocol deviations that may significantly affect the completeness, accuracy, and/or reliability of the trial data or that may significantly affect a patient’s rights, safety, or well-being. For example, important

protocol deviations may include enrolling patients in violation of key eligibility criteria designed to ensure a specific patient population or failing to collect data necessary to interpret primary endpoints, as this may comprise the scientific value of the trial

- Non-important protocol deviations are those that are not considered to significantly affect the efficacy evaluation and hence do not warrant patients' exclusion from the PP set
- Important protocol deviations will be identified by study team review during the DRM prior to database snapshot for main analysis

Additional important protocol deviations may be defined at the DRM prior to data base lock for the main analysis. During the DRM, protocol deviations as specified in this section of the SAP and all protocol deviations as reported in the CTMS system will be evaluated and decided which important protocol deviation will results in an exclusion of a patient from the PP set.

Important and non-important protocol deviations will be presented in a listing. The number and percentage of patients excluded from the PP set will be summarized in total and by protocol deviation type for the ITT set.

7.2.1 Protocol deviations due to COVID-19

Protocol deviations related to COVID-19 are documented in the CTMS with the preface "COVID-19" in the deviation description.

COVID-19 related protocol deviations are, for example:

- COVID-19, Visit xx on date xx of patient not conducted due to site facility re-organization related to COVID-19 disruption
- COVID-19, missing Visit xx due to patient affected by COVID-19

A separate table will be generated summarizing the number and percentage of patients with a COVID-19 protocol deviation. Respective data will be listed.

Protocol deviation due to COVID-19 will be summarized using the ITT set.

7.3 Subgroups

The following subgroups are defined for statistical analysis:

- Age categories (< 50 years, >= 50 - < 65 years , >= 65 years)
- mCRPC patients: Visceral metastasis at study entry (Yes, No)
- mCRPC patients: Prior treatment with Docetaxel or other Taxanes (Yes, No) (use ATC Level 4 Code = L01CD for the derivation)
- LPC patients: PSA level at baseline (<= 20 ng/mL, > 20 ng/mL)
- LPC patients: NCCN Risk Group at diagnosis (Very low risk, Low risk, Intermediate risk, High risk, Very high risk, Unkown)

The definition of subgroups and the respective cut points could be modified for the analysis depending on the enrolled patients. Further subgroups may be defined during the DRM meeting for the final analysis.

Subgroup analyses will be provided for the mITT set (for ORR and PFS per PCWG3), unless otherwise specified.

8 STATISTICAL ANALYSES

8.1 General considerations

In general, the statistical analysis will be performed by trial part (i.e., Part 1 and Part 2) and by treatment group in the Part 2 (i.e., Part 1 mCRPC W_pro1, Part 2 mCRPC W_pro1 + Cemiplimab, Part 2 mCRPC W_pro1, Part 2 LPC W_pro1 + Cemiplimab, Part 2 LPC W_pro1). A detailed description of treatment labels to be used for the analysis is provided in Section 13.4.

For Part 2 of the trial all analyses (disposition, baseline characteristics, efficacy and safety (except adverse event (AE) analysis)) will be analyzed by treatment group and in addition for 3 combined treatment groups “Part 2 Total mCRPC”, “Part 2 Total LPC” and “Part 2 Total”. “Part 2 Total” is an optional treatment group only for some predefined tables.

AE analyses will be analyzed for 6 additional combined treatment groups i.e. “Part 2 Total Monotherapy”, “Part 2 Total Combination Therapy”, “Part 2 Total”, “Parts 1 and 2 Total mCRPC”, “Parts 1 and 2 Total Monotherapy” and “Parts 1 and 2 Total”. A detailed description of all combined treatment groups is available in Section 13.4.

Continuous variables will be summarized by treatment group using the following descriptive statistics: number of patients with non-missing data (n), mean, standard deviation, median, minimum, maximum, lower quartile (Q1) and upper quartile (Q3) where appropriate.

Categorical variables will be summarized by treatment group presenting absolute and relative frequencies (n and %) of patients in each category.

Shift tables from baseline will summarize only cases, where both time points are available, to avoid a “missing” category. The percentages are calculated with respect to the available patients.

Generally, only measurements at scheduled visits will be summarized and included in the tables by visit. Unscheduled measurements will be included in the listings, only.

Time-to-event-endpoints (DoR, PFS, and OS) will be analyzed using Kaplan-Meier methodology and censored in accordance with the US FDA Guidance: “Clinical Trial Endpoints for the Approval of Cancer Drugs and Biologics” [6].

The median survival time (including two-sided 95% confidence limits according to Brookmeyer and Crowley) and the first and third quartiles will be presented for each treatment group. Survival rates (including 95% confidence interval (CI) based on Greenwood's formula) as well as the number and percentage of patients with events,

censored and under risk will be displayed for selected time points (e.g. after 3 months, after 6 months and after 12 months).

The survival distributions for two treatment groups will be compared using the log-rank test, and the p-value will be provided. The associated hazard ratio (HR) and two-sided 95% confidence interval will be estimated by using Cox proportional hazard model with treatment as model covariate.

All treatment comparisons, except the analysis defined for the primary efficacy endpoint see Section 4, are purely exploratory. Exploratory treatment comparisons will be performed separately for patients with mCRPC (comparison of Arm 1A versus Arm 1B) and for patients with LPC (comparison of Arm 2 versus Arm 3).

The time-to-event analysis will be illustrated using Kaplan-Meier plots by treatment groups.

Efficacy data collected for patients in Arm 1B after the switch from W_pro1 monotherapy to cemiplimab monotherapy will not be considered in the efficacy analyses. These measurements will only be considered in the exploratory efficacy analyses comprising ORR, DoR, PFS (per PCWG3 and iRECIST (central reading)) and PFS2 on cemiplimab monotherapy based on last tumor assessment prior to start of cemiplimab treatment. These exploratory endpoints to analyze the preliminary anti-tumor activity of cemiplimab monotherapy will be generated using the subsequent cemiplimab monotherapy on progression set. More details regarding these analyses can be found in Section 8.7.4.2.

The safety and tolerability profile of cemiplimab monotherapy will be analyzed using the subsequent cemiplimab monotherapy on progression set. The definition of cemiplimab TEAEs will be provide in detail in Section 8.9.3. All other safety data (e.g. laboratory, electrocardiogram (ECG), vital signs) reported for patients in Arm 1B after the switch to cemiplimab monotherapy will be included in the respective listings.

All relevant data will be listed. The listing will be sorted by treatment group, patient number and date/time of assessment (if applicable). Unscheduled measurements will be included in the listings.

See Section 11 for the definition of planned summary tables, figures and listings. Templates for each unique table and patient listing are provided in a separate document “Mock Tables, Listings and Figures”.

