# Duration of Response

The DoR is defined as the time from the date of first radiographic documented OR to the date of first disease progression. Only patients who experience a confirmed CR or PR will be analyzed for DoR. DoR will be analyzed using the Kaplan-Meier method. Patients alive and without disease progression at data cut-off date or patients lost to follow-up will be censored at the day of their last tumor assessment. Additional censoring rules will be defined in the SAP.

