8.7.4.1 Exploratory efficacy endpoints

Objective Response Rate based on iRECIST (central reading)

ORR based on iRECIST will be analyzed for mCRPC patients in Part 1 and Part 2 only.

The ORR is defined as the number of patients with iCR or iPR as best objective response per iRECIST divided by the number of patients in the mITT set. Patients not meeting the criteria for iCR or iPR, including those without any post-baseline tumor assessments, will be considered as non-responders. The ORR will be summarized with absolute and relative frequencies along with two-sided 95% Clopper-Pearson CIs by treatment group.

BOR (all categories) will be summarized with absolute and relative frequencies.

Tumor response assessment including overall response and BOR will be listed. In addition, listings including all tumor assessments per iRECIST (central reading) (target lesion, non-target lesion, new lesion) will be generated.

Duration of Response

DoR will be analyzed for Part 1 and Part 2 Arms 1A and 1B only. DoR will be analyzed separately for PCWG3 and iRECIST (central reading).

The DoR is defined as the time from the date of first radiographic documented OR to the date of first disease progression or death from any cause, whichever occurs first. Only patients who experience a confirmed OR will be analyzed for DoR.

In case death date is reported after trial discontinuation date, these death details will not be considered in the DoR analysis. The patient will be censored at the day of the last response assessment.

DoR will be analyzed using the Kaplan-Meier method. Kaplan-Meier plots will be generated.

Patients alive and without disease progression at data cut-off date or patients lost to follow-up will be censored at the day of their last response assessment.

Only response assessments prior to or at the start date of the first subsequent anti-cancer therapy will be considered for DoR analysis. PD within 14 days after the start date of the first subsequent anti-cancer therapy will be considered.

DoR based on PCWG3:

OR is defined as CR or PR. Disease progression is defined as tumor response = Progressive Disease (PD)

DoR expressed in months for patients whose objective response was confirmed CR or PR
= (MIN [Date of first documented disease progression (PD), date of death from any cause]
– Date of first documented overall response (CR or PR) + 1) / 30.4375 for events

or

(Date of the last evaluable response assessment – Date of first documented overall

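### The SAP's general rule puts a between-arm log-rank p-value and hazard ratio on duration of response, which is analysed in responders only and so is not a randomised comparison

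*SAP*

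**What the plan says.** SAP 8.1 sets one rule for the whole class of endpoints: "Time-to-event-endpoints (DoR, PFS, and OS) will be analyzed using Kaplan-Meier methodology". The same section then gives the between-arm analysis, with no exception for DoR: "The survival distributions for two treatment groups will be compared using the log-rank test, and the p-value will be provided". It continues: "The associated hazard ratio (HR) and two-sided 95% confidence interval will be estimated by using Cox proportional hazard model with treatment as model covariate". For metastatic patients the contrast is the "comparison of Arm 1A versus Arm 1B".

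SAP 8.7.4.1 defines who enters the DoR analysis: "Only patients who experience a confirmed OR will be analyzed for DoR". Protocol 9.4.4 agrees: "Only patients who experience a confirmed CR or PR will be analyzed for DoR".

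The DoR text in SAP 8.7.4.1 names only one method: "DoR will be analyzed using the Kaplan-Meier method". The PFS and OS texts in that section also name only Kaplan-Meier, so the log-rank test and hazard ratio reach all three endpoints through SAP 8.1 alone.

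The protocol plans Kaplan-Meier summaries for these endpoints, with no log-rank test or hazard ratio, and its Section 9.1 rules out a formal comparison between arms. SAP 13.1, which lists changes to the protocol-planned analyses, does not mention adding them.

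**The concern.** Randomisation makes Arms 1A and 1B comparable as whole groups. It does not make their responders comparable, because response occurs after treatment starts and treatment can change who responds. A log-rank test confined to responders therefore asks whether two differently selected subgroups have equal durations. It does not ask whether the randomised treatments differ.

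The awkward case is a combination that keeps every durable response the monotherapy would have produced and adds some shorter ones. No patient is worse off, yet the average response in the combination arm becomes shorter and the hazard ratio moves against it.

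At stake is interpretation. Under SAP 8.1 a DoR hazard ratio would be reported in the same way as those for PFS and OS, and nothing in the SAP says that it lacks their randomised basis.

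**Working it through.** **1. The plan's own figure.** No figure is stated for the DoR comparison. The only design figure bearing on responder numbers is the two-stage design in SAP 6: 20 patients, then 33, stopping at 1 or fewer responses and rejecting at 5 or more. With X1 ~ Bin(20, p) and X2 ~ Bin(13, p),

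P(reject) = Σ over x = 2 to 20 of P(X1 = x) × P(X2 ≥ 5 − x).

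This gives 0.802 at p = 0.20 (stated 80%) and 0.0218 at p = 0.05, within the stated 2.5%. The design reproduces.

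**2. Expected responders per arm (n × p).**
- Response rate 5%: 33 × 0.05 = 1.65, or 20 × 0.05 = 1.0. The chance of no responder at all is 0.95^33 = 0.18, or 0.95^20 = 0.36.
- Response rate 20%: 33 × 0.20 = 6.6, or 20 × 0.20 = 4.0.

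The comparison would rest on a handful of patients, and sometimes could not be computed.

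**3. A hand example of the direction.** The durations, in months, are invented for illustration; + marks censoring. Arm 1B has two responders: 10, 12+. Arm 1A has the same two and five short ones: 3, 3.5, 4, 4, 5, 10, 12+. In Arm 1A:

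| Time | Events | At risk, total (1A) | Expected in 1A | Variance |
|---|---|---|---|---|
| 3 | 1 | 9 (7) | 0.778 | 0.173 |
| 3.5 | 1 | 8 (6) | 0.750 | 0.188 |
| 4 | 2 | 7 (5) | 1.429 | 0.340 |
| 5 | 1 | 5 (3) | 0.600 | 0.240 |
| 10 | 2 | 4 (2) | 1.000 | 0.333 |
| Sum | 7 | | 4.556 | 1.274 |

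Observed events in Arm 1A are 6, so O − E = 1.444. Chi-square = 1.444² / 1.274 = 1.64, p = 0.20. The approximate hazard ratio is exp(1.444 / 1.274) = 3.1 against Arm 1A, which has 7 / 2 = 3.5 times as many responders and has lost no durable response.

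**4. How often this could happen.** Simulated trials with exponential durations, censoring at 12 months and a two-sided 5% log-rank test in responders. Both arms have the same rate of durable responders; Arm 1A alone adds short ones. Every rate and duration here is an assumption, because the documents give none. Percentages are of computable trials.

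| Per arm | Durable, both arms | Added in 1A | Points against 1A | p < 0.05 against 1A |
|---|---|---|---|---|
| 33 | 10%, median 12 | 20%, median 3 | about 83% | about 13% |
| 20 | 10%, median 12 | 20%, median 3 | about 78% | about 9% |
| 33 | 10%, mean 12 | 20%, mean 3 | 83% | 14% |
| 33 | 5%, mean 12 | 15%, mean 3 | 78% | 10% |
| 20 | 5%, mean 12 | 15%, mean 3 | 75% | 6% |
| 33 | 10%, mean 9 | 20%, mean 4 | 72% | 8% |
| 33 | 20%, mean 8 | none | 50% | 3% |

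The last row is the control: with no true difference the sign is even. In the 20-per-arm row with 5% durable responders, the test can be computed in only 63% of trials.

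**The case against.** The strongest reply is materiality, and much of it stands. SAP 4 treats p-values outside the primary hypothesis as supportive or explorative, with no statement on significance. SAP 8.1 calls the arm comparisons exploratory, and DoR is an exploratory endpoint. The interim rule uses response counts only. Enrolment to both metastatic arms was stopped after the interim analysis, and the documents give neither final arm sizes nor responder counts. This limits the consequence. It does not cure the selection, since a nominal p-value still needs a null hypothesis that means something for treatment.

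A second reply is that SAP 8.1 was never meant to reach DoR. The mock tables are a separate document and might not print these statistics. But 8.1 names DoR, makes no exception, and is also the only source of the log-rank test for PFS and OS. If DoR was not intended, 8.1 should say so. The rule cannot apply to the single-group analyses of Arm 1B patients who switch to cemiplimab (SAP 8.7.4.2), so the point does not extend to every time-to-event analysis.

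Two stronger readings are tempting, and neither is supported.
- A reader might infer that the DoR test is nearly powerless to show the combination's activity. With response rates of 30% versus 5% and equal 6-month median durations, it rejects in about 8% of trials, against about 79% for a rank test on time in response that counts non-responders as zero. But durations are equal in that scenario, so the 8% is a false-positive rate. The 79% mostly repeats a response-rate comparison (a chi-square test gives 81%), and response rate is already reported by arm with confidence intervals.
- A reader might infer that the DoR result will mislead. That requires the added responses to be shorter, and nothing in the documents shows that they are.

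**Conclusion.** The concern holds in a limited form. As written, SAP 8.1 applies a between-arm log-rank p-value and hazard ratio to DoR. Because DoR is confined to confirmed responders, those statistics are not a randomised comparison of Arms 1A and 1B. This follows from the text and does not depend on any simulation.

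The size of the possible harm does depend on assumptions. Across the mixtures tried, the sign is wrong in 72% to 83% of computable trials, but nominally significant in the wrong direction in only 6% to 14%. The main risk is therefore a misleading point estimate, more than a misleading p-value. No primary conclusion, error rate or stopping decision is affected.

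**What to change.** In SAP 8.1, restrict the between-arm log-rank test and Cox hazard ratio to PFS and OS. State that DoR is summarised descriptively by arm (Kaplan-Meier curve, median with confidence interval, range) with no p-value or hazard ratio. Carry this through Tables 14.2.3.2.x and 14.2.3.3.x, their SAS-output companions and the subgroup versions, and check the mock tables against it.

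The cost is one sentence in the SAP and, if the mock tables print them, removal of two statistics. No new data and no protocol change are needed, since the protocol plans only Kaplan-Meier summaries for DoR.

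No replacement test is needed. A comparison of time in response with non-responders counted as zero should be added only if its analysis set (the SAP's efficacy set is the mITT set) and its handling of censoring at varying last-assessment dates are specified first.

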8.2 Key definitions

Date/time of first administration of IMP (W_pro1 or Cemiplimab):

Is defined as first administration date/time of IMP (W_pro1 or cemiplimab), whichever was administered first.

Baseline Definition:

Baseline is defined as last available value prior to or on the date/time of first administration of IMP (W_pro1 or cemiplimab, whichever was administered first). Unscheduled measurements prior to first administration of IMP will be considered in the calculation of the baseline values. In the case that date/time of first administration of IMP is missing (i.e.,

for randomized not treated patients) the date/time of randomization will be used for the definition of baseline values.

Cemiplimab Baseline – Baseline definition for Arm 1B patients who switch to cemiplimab monotherapy:

Cemiplimab Baseline is defined as last available value prior to or on the date/time of first administration of cemiplimab.

In case no time of the assessment is reported, measurements at the same date as first administration of cemiplimab will be considered as baseline.

Change and percent change from baseline:

Change from baseline will be calculated as follows:

- Change from baseline = post-baseline assessment value – baseline assessment value.
- Percent change from baseline = (post-baseline assessment value – baseline assessment value) / baseline assessment value * 100.

Age (in years) at date of informed consent:

Age is derived in the database based on the collected Year of birth as follows:

Age = ICF Date – (01July + Year of birth) / 365.25.

Age as derived in the database will be used for all analyses.

Body mass index (BMI):

BMI will be calculated as follows:

$$\text{BMI} \left(\frac{\text{kg}}{\text{m}^2} \right) = \frac{\text{Weight (kg)}}{\text{Height(m)}^2}$$

Duration:

Duration will be calculated as follows:

- Duration (days) = last observation date – first observation date + 1

For conversion of days to months or years the following rules will be applied:

- 1 month = 30.4375 days
- 1 year = 365.25 days

Time from first diagnosis to enrollment (in months):

Date of initial diagnosis is collected in Month/Year. Missing day will be replaced with the first day of the month. In case month is not reported, missing month will be replaced with July.

Time from first diagnosis to enrollment (months) will be calculated as:

(ICF date – imputed date of initial diagnosis) / 30.4375

Time from treatment start to post treatment prostatectomy for LPC patients (in days):

For date of prostatectomy or radical prostatectomy, missing day will be replaced with the first day of the month. In case month is not reported, missing month will be replaced with July.

Time from treatment start to prostatectomy (days) will be calculated as:

(Date of prostatectomy – date of first IMP administration (W_pro1 or cemiplimab) + 1

Study day:

Study day is defined as follows:

If date of assessment is on or after the date of first IMP administration (W_pro1 or cemiplimab):

- Date of assessment – date of first IMP administration + 1

If date of assessment is before date of first IMP administration (W_pro1 or cemiplimab):

- Date of assessment – date of first IMP administration

Laboratory values with “< xx” or “> xx”:

Any laboratory values given as “< xx” or “> xx” in the database will be imputed with the numeric value of xx without the sign for the descriptive statistics and the calculation of changes from baseline (e.g., a value of < 1 will be imputed as 1 for the calculations).

Last date known to be alive:

Last date known to be alive is defined as last documented date in the database for the patient, including all visit dates, assessment dates (if different from visit dates), trial treatment administration dates, tumor assessment dates, end of treatment dates, date of trial completion or early trial withdrawal date, start/stop dates of AEs, PSA response date, survival follow-up date (where patients survival status is alive), whichever comes last.

Start of Follow-up Period:

Part 1 and Part 2 mCRPC patients: Follow-up period starts at the administration of the last dose of IMP.

Part 2 LPC patients: Follow-up period starts at the last administration of IMP at Cycle 8 or at administration of the last IMP in case of discontinuation of trial treatment.

Pooling of centers:

No pooling of centers is planned for this trial.

Conventions for imputing missing/partially missing dates:

When computations on dates are to be performed, incomplete/missing dates will be imputed using the following rules.

- Missing day, month/year present: If the month/year is the same as the month/year of the first IMP administration date, then impute missing start dates with first IMP administration date. Otherwise, for dates corresponding to a start date, impute with the first day of the month and, for dates corresponding to a stop date, impute with the last day of the month.
- Missing month/day, year present: If the year is the same as the year of the first IMP administration date, then impute missing start dates with first IMP administration date. Otherwise, for dates corresponding to a start date, impute with the first day of the year and, for dates corresponding to a stop date, impute with the last day of the year.
- Missing month/day/year: no imputation.
- In case imputed start date is after available stop date, the imputed start date will be replaced with the stop date to avoid negative durations.

This imputation method will be applied to the following dates:

- Onset date of AEs (for treatment-emergent purpose), incomplete AE end dates
- Medical history start date to define prior medical history and concomitant diseases
- Date of prior/concomitant medication (start dates) to define prior and concomitant medication, incomplete stop dates of prior/concomitant medications

Conventions for imputing missing/partial start dates of the subsequent anti-cancer therapy:

- If the start date of the first subsequent anti-cancer therapy is missing, it will be imputed with the date of the End of Treatment (EoT) visit.
- Missing day, month/year present: If the month/year is the same as the month/year of the EoT visit date, then impute missing start dates with EoT visit date. Otherwise, for dates corresponding to a start date, impute with the first day of the month and, for dates corresponding to a stop date, impute with the last day of the month.
- Missing month/day, year present: If the year is the same as the year of the EoT visit date, then impute missing start dates with the EoT visit date. Otherwise, for dates corresponding to a start date, impute with the first day of the year and, for dates corresponding to a stop date, impute with the last day of the year.
- If the EoT visit date is missing, the date of the last study treatment administration + 14 days to be used for the imputation.
- In case imputed start date is after available stop date, the imputed start date will be replaced with the stop date to avoid negative durations.

Clinical progression:

Clinical progression reported more than 14 days after start of the first subsequent anti-cancer therapy will not be considered in the analysis of clinical progression.

Best Overall Response (BOR) based on Radiological Soft Tissue Evaluation:

The BOR is defined as a single best response status at any tumor response assessment after first administration of IMP and prior to or at the start date of the first subsequent anti-cancer therapy. Overall response of PD within 14 days after the start date of the first subsequent anti-cancer therapy will be considered.

Only responses up to and including the date of the first progressive disease will be considered in the derivation of the BOR.

The following order of tumor response categories will be used, with “Complete Response” is the best category:

Complete Response (CR) – Partial Response (PR) – Stable Disease (SD) – Progressive Disease (PD) – Not Evaluable (NE) – Not Applicable (NA).

Best Overall Response (BOR) based on iRECIST (central reading):

The following order of tumor response categories will be used to define the BOR category based on iRECIST (central reading), with “Complete Response” is the best category:

Complete Response (iCR) – Partial Response (iPR) – Stable Disease (iSD) - Unconfirmed Progressive Disease (iUPD) – Confirmed Progressive Disease (iCPD) – Not Evaluable (NE) – Not Applicable (NA).

Only central reading assessments after first administration of IMP and prior to or at the start date of the first subsequent anti-cancer therapy will be considered in the derivation. Overall response of iUPD or iCPD within 14 days after the start date of the first subsequent anti-cancer therapy will be considered.

Only responses up to and including the date of the first progressive disease will be considered in the derivation of the BOR.

Further information on the definition of the BOR based on iRECIST is available in Section [13.3](#).

PSA Response definition based on PCWG3:

PSA response definition based on PCWG3 will be derived based on the PSA response data reported by the investigator.

If a PSA PD occurred \geq 12 weeks after first administration of IMP. This PSA PD needs no confirmation.

For the derivation of best overall PSA Response based on PCWG3, the PSA responses have to be **confirmed**. The following rules have to be implemented for PSA response confirmation:

- **PSA PR Response Confirmation**
 - PSA PR needs to be confirmed by:
 - Subsequent [Radiological Soft Tissue PR or CR response] or
 - Subsequent [PSA PR response]

- Which occurs within ≥ 20 days and \leq start date of first subsequent anti-cancer therapy, immediately after initial PSA PR response
 - With no worse response (SD, PD) between initial PR and confirmation response
 - Worse responses are defined as [Radiological Soft Tissue SD or PD response] or [Clinical Progression Event] or [Progressive Bone Disease] or [PSA SD or PD response]
- **PSA SD Response Confirmation**
 - PSA SD needs to be confirmed by:
 - Subsequent [Radiological Soft Tissue SD, PR or CR response] or Subsequent [PSA SD or PR response]
 - Which occurs within ≥ 20 days and \leq start date of first subsequent anti-cancer therapy, immediately after initial PSA SD response
 - With no worse response (PD) between initial SD and confirmation response
 - Worse responses are defined as [Radiological Soft Tissue PD response] or [Clinical Progression Event] or [Progressive Bone Disease] or [PSA PD response]
 - **PSA PD Response Confirmation**
 - If a PSA PD occurred < 12 weeks after first administration of IMP, this PSA PD needs to be confirmed by:
 - Another PSA PD that occurred immediately after the initial PSA PD and ≥ 12 weeks after first administration of IMP and \leq start date of first subsequent anti-cancer therapy + 14, immediately after the initial PSA PD response.
 - Subsequent [Radiological Soft Tissue PD] or [Clinical Progression] or [Progressive Bone Disease] immediately after the initial PSA PD and \leq start date of first subsequent anti-cancer therapy + 14.
 - PSA PD confirmation can only occur if there are no better responses (CR, PR, SD) between the initial PSA PD and confirmation assessment.
 - Better responses are defined as [Radiological Soft Tissue CR, PR or SD response] or [PSA PR, SD response]

Best Overall PSA Response definition based on PCWG3:

The best overall PSA response based on PCWG3 is defined as a single best PSA **confirmed** response status at any response assessment after first administration of IMP and prior to or at the start date of the first subsequent anti-cancer therapy. Overall response of PD within 14 days after the start of the first subsequent anti-cancer therapy will be considered.

Only responses up to and including the date of the first progressive disease will be considered in the derivation of the best overall PSA Response.

The following order of response categories will be used, with “Partial Response” is the best category:

Partial Response (PR) – Stable Disease (SD) – Progressive Disease (PD) – Unknown – Not Applicable (NA).

Best Overall Response (BOR) based on PCWG3:

The rules for the definition of BOR based on PCWG3 are referring to the following data reported in the CRF:

- Confirmed PSA response reported by the investigator (see Section 8.2 for more details regarding PSA response confirmation)
- Radiological Soft Tissue Evaluation (response data collected in the CRF on the “RECIST 1.1” page)
- Clinical Progression (data collected in the CRF on the “Clinical Progression” page)
- Bone Disease Progression (data collected in the CRF on the “Bone Lesion” pages with Clinical Impression = Progression)

Only assessments after first administration of IMP and prior to or at the start date of the first subsequent anti-cancer therapy will be considered in the derivation. Overall response of PD within 14 days after start date of the first subsequent anti-cancer therapy will be considered.

Only responses up to and including the date of the first progressive disease will be considered in the derivation of the BOR.

Overall Response of CR, PR, SD per PCWG3 is based on radiological soft tissue response or confirmed PSA response.

Progression of Disease per PCWG3 is based on the earliest radiological soft tissue progression, Bone disease progression, confirmed PSA progression or clinical progression.

The following order of tumor response categories will be used, with “Complete Response” is the best category:

Complete Response (CR) – Partial Response (PR) – Stable Disease (SD) – Progressive Disease (PD) – Not Evaluable (NE) – Not Applicable (NA).

Derivation of PSADT:

PSADT will be derived based on the PSA measurements provided by the investigator in the database and collected during the trial at screening visit and during each cycle.

PSADT will be calculated post-treatment on C4D1 and D1 of every fourth subsequent cycle (e.g. C8D1, C12D1, etc.) in Part 1 and Part 2 Arms 1A and 1B, or on C4D1, C8D1, and EoT in Part 2 Arms 2 and 3.

PSA measurements reported after EoT visit or after start of the first subsequent anti-cancer therapy will not be considered in the derivation of PSADT.

PSADT will be calculated using a linear regression model of the natural logarithm of PSA values and time ([3] and [<https://drhaddad.com.au/wp-content/uploads/2022/07/13.pdf>], [8]).

Derivation of PSADT post-treatment at every fourth subsequent cycle:

1. Compute the slope of the regression line of natural logarithm of PSA vs. time (which is the number of doublings per unit time) where PSA is the PSA level in ng/mL at each time point
2. Compute PSADT (days) = natural log (2) / slope,
natural log (2) = 0.693.
3. Multiply PSADT (days) by 12/365.25 to get PSADT (months)

The calculation of post-treatment PSADT should be based on (1) at least 3 consecutive PSA values with each value ≥ 0.2 ng/dL (or ≥ 0.002 ng/mL), (2) inclusion of the most recent PSA values during androgen deprivation therapy, and (3) interval between first and last PSA value of ≥ 8 weeks but ≤ 12 months.

